11.2.6 Safety Analyses

Safety analysis will be performed on the safety population using descriptive statistics without inferential tests for significance. Safety evaluation will include monitoring of adverse events (adverse events/SAEs). Adverse events will be coded using the current version of the Medical Dictionary for Regulatory Activities (MedDRA). Treatment-emergent adverse events will be presented in summary tables by system organ class (SOC), preferred term and by treatment group. The number and percentage of subjects within each SOC and preferred term and the number of adverse events within each SOC and preferred term will be presented. The summary of adverse events by severity (mild, moderate, or severe) will be tabulated. The summary of adverse events by causality (possibly related, related, unknown) will also be provided. For each patient and each adverse event, the worst severity and causality recorded will be used in the by-intensity and by-relationship summaries.

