5.3 Safety Assessments

Safety assessments will include evaluation of the frequency and nature of adverse events (AEs) and adverse device effects (ADEs) up to 30 days after treatment application.

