7.2 Study Treatment Day 0 (Visit 2 – Surgery)

On Day 1, eligible subjects will report to the hospital/surgical site at the scheduled time. Prior to surgery, the following procedures will be performed:

- Review of inclusion and exclusion criteria; and
- Review and record any changes to concomitant medications.

Other procedures will be performed in accordance with the pre-surgical and surgical site standards.

During the surgical procedure, subjects with appropriate target bleed sites (TBS) as determined using the validated bleeding severity scale (see [Section 8.6](#)) will be randomized to their assigned treatment (HemoStyp or Surgicel).

Each treatment will be applied in accordance with technical instructions provided in the investigator manual. Upon application of the study treatment at target bleeding site, a stopwatch will be started with inspection for bleeding occurring every 30 seconds for 10 minutes. In addition, the investigator will inspect the target bleeding site for 5 minutes after hemostasis is presumed to be achieved to ensure rebleeding does not occur.

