9.2 Collection of Adverse Events and Adverse Effect Information

All adverse events and adverse effects, serious and non-serious, will be collected from the time a subject signs the informed consent through the last study visit. Clinical study subjects will be routinely questioned about adverse effects at study visits.

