9.8 Reporting Adverse Events

The Investigator is required to report all adverse events experienced by the patient from the day of the surgical procedure (Visit 2) until the patient completes Visit 3 (30 days after the surgical procedure) or withdraws early (prior to Visit 3). All adverse events (both serious and non-serious), regardless of their relatedness to the study device or procedure, must be reported in the Adverse Event eCRF. The investigator will evaluate the severity of the event, and its relatedness to the study device or procedure. Both severity and relatedness of all adverse events need to be entered in the Adverse Event eCRF.

Any necessary medical management of the event will be recorded in the patient's medical record/source document. All adverse events must be followed until resolution or until they become stable but ongoing.

The Investigator will record all adverse events (both serious and non-serious) in the source documents. Standard medical terminology should be used when recording adverse events. In addition, the following information should be recorded:

- Onset date
- Resolution date or date of death
- Severity of the event
- Action taken
- Event status (ongoing at study end or resolved)
- Relationship of adverse event to the device used in the study
- Relationship of the adverse event to the study surgical procedure
- Indication of whether the event is serious.

Data related to SAEs will be collected until event resolution, or until the event is considered stable, or until all attempts to determine the resolution of the event are exhausted. All adverse events that are unresolved at study completion (or early termination) will be recorded as ongoing at study end.

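### Section 9.8 lists only an onset date for adverse events, so non-serious Day 0 events cannot be placed before or after mid-operation application, which dilutes the treatment-emergent tables to an unknown degree

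*Combined protocol and SAP*

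**What the plan says.** Section 11.2.6 sets out the safety output: "Treatment-emergent adverse events will be presented in summary tables by system organ class (SOC), preferred term and by treatment group". It adds that "Safety analysis will be performed on the safety population using descriptive statistics without inferential tests for significance". Neither that section nor any other defines treatment-emergent or gives its starting point. The nearest thing to an origin is section 5.3, which counts safety follow-up "up to 30 days after treatment application".

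Randomization and application happen inside the operation. Section 7.2 begins the step with "During the surgical procedure, subjects with appropriate target bleed sites (TBS) as determined using the validated bleeding severity scale", and those subjects are then randomized and treated. Sections 6.1 and 8.7 require that conventional hemostasis has already been found ineffective or impractical.

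Section 9.8 has events reported "from the day of the surgical procedure (Visit 2) until the patient completes Visit 3" and lists the items to record for each. The start of the event appears as a date. The list has no clock time and no item that places the event before or after application. It does include "Relationship of adverse event to the device used in the study" and, separately, the relationship to the surgical procedure.

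Section 9.2 gives a different start for collection: events "will be collected from the time a subject signs the informed consent through the last study visit".

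**The concern.** Anaesthesia, incision, the main procedure and the failed attempts at conventional hemostasis all come before study treatment, usually on the same calendar day. Events arising in that period cannot be caused by either hemostat. If Day 0 events carry only a date, an analyst who must build treatment-emergent tables has no listed item with which to remove them, and the simplest rule (onset on or after the date of treatment) keeps them all.

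Safety is part of the stated objective in section 3, and section 2 describes the purpose as comparing both efficacy and safety with Surgicel. Because the safety analysis is descriptive, readers will judge the devices from the tabulated percentages. Device-irrelevant events added to both columns make the arms look more alike in relative terms.

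A later SAP, which section 11 promises before database lock, can supply the definition. It cannot supply an order of events that was not recorded.

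**Working it through.** The documents state no adverse event rates and no safety figure, so there is nothing to reproduce. The check has two parts.

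**Part 1: can a Day 0 event be classified from the listed data?**

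- Needed: the order of event onset and first application.
- Application: on Day 0, during surgery (section 7.2). The stopwatch started at application times the bleeding inspections; nothing links it to adverse event onset.
- Event onset: date only (section 9.8).
- Events dated before Day 0 or after Day 0 can be classified from the date. Events dated Day 0 cannot.
- Serious events: section 9.8.1 requires a narrative that covers onset, so the order may be recoverable. Non-serious events have no such requirement.

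**Part 2: what does a date-based rule do to the tables?**

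Let *p* be the risk of at least one post-application event in an arm, and *b* the risk of at least one Day 0 pre-application event, taken as equal in both arms and independent of *p*. Then:

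- tabulated risk = 1 − (1 − *p*)(1 − *b*)
- tabulated difference = (*p*_H − *p*_S)(1 − *b*)
- 95% half-width = 1.96 × √[*a*(1 − *a*)/106 + *c*(1 − *c*)/106], where *a* and *c* are the tabulated risks for HemoStyp and Surgicel and 106 is the arm size in section 11.1

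All values of *p* and *b* are assumptions. With *p* = 20% (HemoStyp) and 10% (Surgicel):

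| *b* | HemoStyp | Surgicel | Ratio | Difference (points) | 95% half-width (points) |
|---|---|---|---|---|---|
| 0% | 20.0% | 10.0% | 2.00 | 10.0 | 9.5 |
| 5% | 24.0% | 14.5% | 1.66 | 9.5 | 10.5 |
| 10% | 28.0% | 19.0% | 1.47 | 9.0 | 11.4 |
| 20% | 36.0% | 28.0% | 1.29 | 8.0 | 12.5 |
| 30% | 44.0% | 37.0% | 1.19 | 7.0 | 13.2 |

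For example, at *b* = 20%: 1 − 0.80 × 0.80 = 0.36 and 1 − 0.90 × 0.80 = 0.28; the ratio is 0.36/0.28 = 1.29 and the difference is 0.10 × 0.80 = 0.08.

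With assumed risks of 10% and 5%, the ratio falls from 2.00 to 1.31 at *b* = 10% and to 1.10 at *b* = 30%.

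The row *b* = 0% is what the table would show if pre-application events were removed.

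These figures describe an any-event proportion. Section 11.2.6 plans rows by system organ class and preferred term. The same formula applies to each row with that row's own *b*. Where a term never occurs before application, *b* = 0 for that row and nothing changes.

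**The case against.** The strongest case against has four parts.

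1. *The information may exist elsewhere.* The section 9.8 list concerns what is recorded in source documents. The eCRF specification is not among the documents, so the form may hold more. Source records are retained and open to verification, and serious events carry a narrative. This stands in part. A reader might infer that Day 0 events can never be separated or that the loss is beyond repair; the documents do not support that. They also do not guarantee times for non-serious events, and a retrospective search would be unplanned work in an open-label trial, done with the arm known.

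2. *The relationship fields help.* An event known to precede application can be judged unrelated to the device. This too is partial. The section 9.7 definitions run device and procedure together, the categories in 9.7 and 11.2.6 include none for unrelated, and attribution is an unblinded judgment, whereas sequence is a fact.

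3. *No arm is favoured and no test is affected.* Randomization follows identification of the bleeding site, so events before it balance in expectation. The analysis is descriptive and has no safety margin. This stands in full. A reader might infer bias toward HemoStyp, or that a real difference would be hidden. Neither follows: in the illustration at *b* = 20% the excess is still 8 points against 10.

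4. *The definition belongs in the SAP, and section 5.3 already implies the origin.* True of the definition. It does not answer the data-capture point, which has to be settled before events are recorded.

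**Conclusion.** The point holds as a cheap improvement to data capture and definition. On the listed items, a non-serious Day 0 event cannot be placed before or after application, and treatment-emergent has no stated meaning that would settle it. A date-based rule would add pre-application surgical and anaesthetic events to both arms.

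The consequence is non-directional dilution and noise: ratios move toward 1, differences shrink modestly and intervals widen. The size is unknown. Under the assumed 20% against 10%, a 5% to 30% background gives ratios of 1.66 to 1.19 and differences of 9.5 to 7 points, in place of 2.0 and 10. This rests on equal and independent background risk in the two arms, on rates that the documents do not give, and on an any-event summary. At preferred-term level the effect is confined to terms that also occur before application.

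The conflict over when collection starts is a separate matter. Events dated before the day of surgery can be excluded by date, so it neither causes nor worsens the Day 0 problem.

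**What to change.** - For Day 0 events, add to the section 9.8 list and the adverse event eCRF either an onset time (with the time of first application also recorded) or one item stating whether onset was before or after first application of study treatment.
- In section 11.2.6, define treatment-emergent as onset at or after first application, in line with the window in section 5.3.
- List pre-application events separately by arm, outside the treatment-emergent tables.
- As a separate correction, reconcile the start of collection: consent in section 9.2 against the day of surgery in section 9.8 and Table 1.1.

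The cost is one eCRF item and a few sentences of text. The downside is one more item for sites to complete on Day 0 events.

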A two-sided z-test with pooled variance will be used to test the difference for each secondary endpoint. The 95% confidence intervals (CIs) for each secondary endpoint in each group (HemoStyp or Surgical) will be provided. The secondary endpoints will be assessed at the significant level of 0.05 in a defined order after achievement of a significant result for the primary endpoint .

To assess homogeneity of treatment effectiveness, subgroup analyses will be performed.

Interim Analysis

After 118 randomized subjects have been seen at 30 day visit.

Safety Analyses

Safety analysis will be performed on the safety population using descriptive statistics without inferential tests for significance. Safety evaluation will include monitoring of adverse events (adverse events/serious adverse events [SAEs]) and adverse device effects (ADEs). Adverse events will be coded using the current version of the Medical Dictionary for Regulatory Activities (MedDRA). Treatment-emergent adverse events will be presented in summary tables by system organ class (SOC), preferred term and by treatment group. The number and percentage of subjects within each SOC and preferred term and the number of adverse events within each SOC and preferred term will be presented. The summary of adverse events by severity will be tabulated. The summary of adverse events by causality will also be provided. For each patient and each adverse event, the worst severity and causality recorded will be used in the by-intensity and by-relationship summaries.

Table 1.1 Schedule of Evaluations

	Screening	Surgery	Post-surgical Follow Up
Visit	V1	(Randomization) V2	V3
Trial Day	Day -10 to 0	Day 0	Day 30 ± 7
Informed consent	X		
Inclusion / Exclusion criteria	X	X	
Demographics	X		
Medical history	X		
Concomitant medication review	X	X	X
Vital signs	X		
Height and Weight	X		
Laboratory Measures ¹	X		
Urine pregnancy test ²	X		
Surgery performed		X	
Appropriate target bleeding sites identified ³		X	
Randomization		X	
Treatment applied to target bleeding sites		X	
Time to hemostasis of target bleeding sites		X	
Assess for re-bleeding or post-surgical re-bleeding		X-----X	X
Adverse events review		X	X

1. Laboratory parameters obtained for subjects as pre-operation standard of care that include a complete blood count (CBC) and may include prothrombin time (PT) and partial thromboplastin time (PTT) reflecting patients medical and medication history.

2. Obtained for women of child-bearing potential.

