9.7 Adverse Event Causality

It is the Investigator's responsibility to assess the relationship between all adverse events and the study procedure. Only adverse events attributable (relationship of possibly, related, or unknown) to a device or the study procedure are to be recorded in the eCRF.

- Possibly: A clinical event (including abnormal laboratory result) that presents an unlikely association between device/procedure, which cannot be ruled out with certainty, but could also be explained by alternative etiology.
- Related: A clinical event (including abnormal laboratory result) that presents a strong temporal relationship between device/procedure, in which an alternative etiology is unlikely.
- Unknown: A clinical event (including abnormal laboratory result) that cannot be determined to be related or unrelated to device/procedure given the information obtained.

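### Section 11.2.6 omits adverse device effects and plans one causality summary without saying which relationship it uses, so no device-related summary by arm is pre-specified

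*Combined protocol and SAP*

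**What the plan says.** Section 5.3, under Study Endpoints, calls for "evaluation of the frequency and nature of adverse events (AEs) and adverse device effects (ADEs) up to 30 days after treatment application", and the synopsis repeats this. The synopsis text on safety analyses says: "Safety evaluation will include monitoring of adverse events (adverse events/serious adverse events [SAEs]) and adverse device effects (ADEs", closing the list there. The matching sentence in section 11.2.6 stops sooner: "Safety evaluation will include monitoring of adverse events (adverse events/SAEs".

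Section 11.2.6 then plans one attribution table: "The summary of adverse events by causality (possibly related, related, unknown) will also be provided". For each patient and event, "the worst severity and causality recorded will be used in the by-intensity and by-relationship summaries".

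Section 9.7 makes it the investigator's task to "assess the relationship between all adverse events and the study procedure"; its next sentence extends to events attributable to a device or to the procedure. It gives three levels (possibly, related, unknown), each defined against device and procedure as one joint item. Section 9.8 lists the items to record as two: "Relationship of adverse event to the device used in the study" and, separately, the relationship to the surgical procedure. Section 9.1 defines an unanticipated adverse device effect but not an ADE.

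**The concern.** Every subject has open thoracic, abdominal or vascular surgery (section 6.1), so events attributable to the operation can be expected in both arms whichever gauze is used. If the causality table does not separate device from operation, its 'related' row may describe the surgery as much as the product. The ADE assessment in section 5.3 would then have no table that reports it.

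This matters for the trial's purpose. The Introduction states that the study supports a PMA application and evaluates safety against Surgicel. It is also a matter of data collection: if sites rate causality on a joint scale, the device judgement may not be recoverable afterwards.

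**Working it through.** The plan attaches no figure to this point, so the check compares sections.

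1. **Stated assessment against analysis text.** Section 5.3 and the synopsis include ADEs. The synopsis analysis sentence includes them; the same sentence in 11.2.6 does not. No section specifies an ADE table or a device-related table.

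2. **Tracing one event.** Take an event that the investigator attributes to the surgery and not to the gauze. Section 11.2.6 does not say which rating feeds its table, so each possible reading is followed:

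| Reading of 11.2.6 | Where the event is counted |
|---|---|
| One joint device/procedure rating, as 9.7 words it | Related |
| Two ratings as in 9.8, worst taken across both | Related |
| Procedure rating only | Related |
| Device rating only | No correct level: possibly, unknown or blank |

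Only the last reading keeps the event out of the 'related' row. It is not the one stated, and it still leaves the event without a valid level.

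3. **Deriving ADEs from the existing levels.** Suppose an ADE were any event whose device relationship is possibly, related or unknown. Those are all the levels in 9.7 and 11.2.6. Every event with a completed device rating would be an ADE, and the ADE table would reproduce the table of all rated events. A 'not related' level is needed before an ADE can be counted.

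4. **Which events reach the database.** Section 9.7 limits the eCRF to events attributable to a device or the procedure. Section 9.8 requires all events there regardless of relatedness. Under 9.7 an unrelated event never appears; under 9.8 it must appear but has no level.

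5. **What is tabulated by arm.** Section 11.2.6 gives treatment-emergent events by system organ class, preferred term and treatment group. Section 11.2.1 calls for all safety variables by treatment group. Together these put whatever is tabulated into columns by arm. They do not define an ADE or choose a relationship.

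6. **Size.** Suppose a share p of subjects in each arm has a procedure-related event, shares d1 and d2 have a device-related event, and the two are independent. A combined row for subjects with any such event would then differ between arms by [1 − (1 − p)(1 − d1)] − [1 − (1 − p)(1 − d2)] = (1 − p)(d1 − d2). The difference shrinks by the factor 1 − p. The documents give none of p, d1 or d2. The worst-causality rule also works per patient and per event, so the formula does not describe rows by preferred term. No number can be put on it.

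**The case against.** - **Section 11 is an overview, and a detailed SAP is to follow.** With 11.2.1 requiring safety variables by treatment group and by-patient listings of all data, a reader should not conclude that device-related events will never be compared. That stands. But the SAP need only be approved before database lock. The trial is open-label, with an interim analysis after 118 subjects reach the 30-day visit, so an ADE definition could be settled after arm-level data are known. Nor can a SAP separate ratings collected on a joint scale.
- **Nothing says the two relationships are merged.** The worst-causality rule can be read as covering repeated records of one event. That stands: merging is the likely reading, given the joint levels and the single summary, but it is an inference.
- **ADEs are not dropped from the protocol.** The synopsis analysis text keeps them. That stands; the omission is in 11.2.6.
- **Other safety contrasts exist.** A reader might infer that device attribution is the only safety comparison available. It is not. All-cause events are tabulated by arm without relying on unblinded attribution, and re-exploration for re-bleeding is a secondary endpoint compared between arms. Neither gives the frequency of ADEs.
- **Section 9.7 is not confined to the procedure.** Its second sentence mentions a device. That stands, but it joins the two and does not ask for separate ratings.

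**Conclusion.** The point holds as a gap between a stated safety assessment and its analysis. Section 11.2.6 omits ADEs and leaves the basis of its one causality summary unstated. The levels are joint and lack 'not related'. No device-related summary by arm is therefore pre-specified, and procedure-related events can enter the 'related' row.

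A reader might go further and infer that the plan would mask a large difference between the two gauzes. The documents do not support that: they contain no adverse event or ADE rates, and a device-related event under its own preferred term would still show by arm. Any safety comparison here is descriptive in any case, and the primary efficacy conclusion is unaffected.

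The conclusion assumes that the three levels in 11.2.6 are those defined in 9.7. It also assumes that the detailed SAP, which is not part of the document, has not already settled the matter. The change is worth making before further causality ratings are collected.

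**What to change.** 1. In 11.2.6, restore ADEs to the safety evaluation, in line with the synopsis.
2. In 9.7, ask for relationship to the device and relationship to the procedure separately, word the levels for each, and add a 'not related' level.
3. In 9.1, define an ADE as an adverse event whose device relationship is anything other than 'not related'.
4. In 11.2.6, replace the single causality summary with two, by arm in the safety population: device relationship and procedure relationship. Take the worst causality within each field, not across them.
5. Reconcile 9.7 with 9.8 on whether unrelated events enter the eCRF.

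The cost is small: wording changes and one extra table. It may also include an added eCRF field and level. Section 9.8 lists the two separate items under what is recorded in source documents, while its eCRF sentences speak only of relatedness to device or procedure, so separate eCRF fields are not established.
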